### 10.16.2.2 Arm A Only: Pregnancies in Female Partners of Male Patients

For patients treated with bempegaldesleukin, any pregnancy occurring during the course of the study and for 3 months after the last dose of bempegaldesleukin in a female partner of a male patient must be reported to the Sponsor. The Sponsor must be notified immediately without undue delay, under no circumstances later than 24 hours following knowledge of the initial report and any follow-up information. All reports should be submitted via the Pregnancy Notification Form. In order for the Sponsor or designee to collect any pregnancy surveillance information, the pregnant patient or partner must sign an informed consent form (See Section 14.2).

Pregnancy, although reportable, is not considered an AE/SAE unless a female partner of a male patient experiences signs or symptoms of pregnancy complications; however, the contact information for pregnancy reporting is the same as for SAE reporting and listed in Section 10.7. Attempts should be made to collect and report details of the course and outcome of any pregnancy in the partner of a male patient exposed to study drug with the authorization from the pregnant partner. Pregnancy follow-up should describe the outcome of the pregnancy, including any voluntary or spontaneous termination, details of the birth, and the presence or absence of any congenital abnormalities or birth defects in the offspring. Pregnancy outcomes of ectopic pregnancy, spontaneous abortion, missed abortion, benign hydatidiform mole, blighted ovum, fetal death, intrauterine death, miscarriage, and stillbirth must be reported as serious events (Important Medical Events). If the pregnancy continues to term, the outcome (health of infant) must also be reported.

## 10.17 Emergency Medical Support and Patient Card

Patients enrolled in this clinical trial will be provided with Emergency Medical Support cards during their trial participation, which will be furnished by the Sponsor. The Emergency Medical Support card is based on the need to provide clinical trial patients with a way of identifying themselves as participating in a clinical trial, and subsequently to give health-care providers access to the information about this participation that may be needed to determine the course of the patient's medical treatment.

This service is designed to provide information to healthcare providers who are not part of the clinical trial. Clinical trial Investigators, who are already aware of the clinical trial protocol and treatment, have other means of accessing the necessary medical information for the management of emergencies occurring in their patients.

The first point of contact for all emergencies will be the clinical trial Investigator caring for the affected patient. The Investigator agrees to provide his or her emergency contact information on the card for this purpose. If the Investigator is available when an event occurs, he/she will answer any questions. Any subsequent action will follow the standard processes established for the Investigators. In cases where the Investigator is not available, the Sponsor will provide a 24-hour

contact number, whereby healthcare providers are given access to a physician designated by the Sponsor who can assist with the medical emergency.

### **10.18 Clinical Laboratory Tests**

Clinical laboratory tests will be conducted according to the Schedule of Events (Section 1.2). A list of the clinical laboratory analytes to be tested is provided in [Appendix 1](#).

Clinical laboratory tests will be performed by the central laboratory. For randomization, if the central laboratory tests are cancelled, lost, or considered inadequate for analysis, the site may forward an identical set of local laboratory samples for eligibility review (with central laboratory testing repeated prior to the first dose of study drug). If local laboratory results are determined to be acceptable during eligibility review, randomization may proceed. Additional clinical laboratory tests may be ordered at the Investigator's discretion.

The Investigator will review all laboratory results for clinical significance. Any laboratory result deemed clinically significant (ie, is associated with signs and symptoms, requires treatment, or requires follow up) will be recorded as an AE as described in Section 10.1.

### **10.19 Physical Examinations**

Physical examinations should be conducted according to the Schedule of Events (Section 1.2).

Full physical examinations evaluate all major organ systems, including the following categories: general, head, eyes, ears, mouth/throat, neck, heart, lungs, abdomen, lymph nodes, joints, extremities, integumentary, and neurologic. Targeted physical examinations are at the discretion of the Investigator to identify changes from baseline or evaluate changes based on the patient's clinical symptoms.

### **10.20 Vital Signs**

Vital sign measurements will be recorded according to the Schedule of Events (Section 1.2). Vital signs include pulse rate, respiratory rate, systolic and diastolic blood pressure, and temperature. It is preferred that the same arm be used for all blood pressure readings, if possible. Weight is to be reported at each vital sign visit, height at screening visit only.

### **10.21 Electrocardiograms**

All patients will have 12-lead electrocardiogram (ECG) done during Screening as specified in the Schedule of Events (Section 1.2). ECG data will be locally assessed. On-treatment ECGs should be obtained if clinically indicated.

### **10.22 Echocardiograms**

Standard echocardiogram will be performed at screening to assess cardiac function and LVEF according to the Schedule of Events (Section 1.2). A MUGA scan can be performed to assess

cardiac function and LVEF if a standard echocardiogram cannot be performed. After randomization, patients with clinically significant cardiac toxicity should have this assessment repeated as indicated.

## 11.0 STATISTICAL PLAN

### 11.1 General Considerations

In general, continuous data will be summarized by descriptive statistics, including number of patients, mean, standard deviation, median, minimum, and maximum. Categorical data will be summarized by the number and percentage of patients. Unless otherwise specified, data will be summarized by treatment arm.

All efficacy evaluations will be analyzed using the intent-to-treat (ITT) population unless otherwise specified, and all safety endpoints will be summarized using the Safety population. In general, the following three stratification factors will be used in stratified analysis in comparing response rates and survival curves of the two arms (bempegaldesleukin plus pembrolizumab versus pembrolizumab), and in Cox proportional hazard analysis unless otherwise specified: disease status (metastatic vs recurrent only), PD-L1 tumor expression (CPS  $\geq$  20 vs CPS 1-19) and HPV status (positive vs negative).

The detailed description of analysis methods will be provided in the statistical analysis plan (SAP).

### 11.2 Determination of Sample Size

The sample size of the study accounts for the following two primary efficacy endpoints: ORR and OS. The overall alpha for this study is 0.05, which is split into 0.001 to evaluate ORR and 0.049 to evaluate OS. All alpha levels are two-sided. At the first interim analysis (Interim Analysis 1 [IA1]), ORR will be analyzed at least one month after the last patient of the Phase 2 portion has been randomized into the study. IA2 will occur when at least 231 OS events have been observed. ORR and OS will be analyzed at IA2 for efficacy and OS will be analyzed for efficacy at the final analysis (FA).

In addition, a fallback approach will be used to reallocate the alpha from ORR to OS. If ORR is significant in favor of the combination of bempegaldesleukin and pembrolizumab, the alpha of 0.001 will be passed to OS. OS can then be tested at 0.05 (instead of 0.049) level. The testing procedure of ORR and OS is described in [Figure 2](#). A total of approximately 500 patients will be randomized into the two treatment arms (bempegaldesleukin plus pembrolizumab versus pembrolizumab) in a 1:1 ratio.

**Figure 2: Statistical Testing Procedure**

IA = Interim Analysis; †

Abbreviations: ~ = approximately;  $\Delta$  = change; FA = final analysis; GNG = go no go decision; IA = interim analysis; IA1 = Interim Analysis 1 (first interim analysis); IA2 = Interim Analysis 2 (second interim analysis); mos. = months; ORR = objective response rate; OS = overall survival; p = p-value

**11.2.1 Sample Size Justification for ORR**

It is projected that IA1 will occur approximately 14 months after the first patient's randomization date (10 months of accrual of 200 patients in both arms, one month of ORR follow-up, and 3 months for data cleaning). IA1 is for ORR futility assessment.

Given a two-sided family-wise error rate of 0.001, 500 patients in the ITT population will provide approximately 96% power to detect a 20% difference in ORR between the 2 treatment arms using a Chi-square test at IA2, assuming an ORR of 19% for pembrolizumab (Burtness 2019). If the observed ORR difference at IA2 is greater than 13.1%, the result will be statistically significant.

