**Table 1: Schedule of Events (Excluding Pharmacokinetic, Immunogenicity, [REDACTED] Sampling) (Contd)**

Procedure / Period:	Screening	Treatment Cycles (3-Week Cycles)					Post-treatment		
		Cycle 1 Only			Cycle 2 and Beyond		Follow-up Visit 1 y	Follow-up Visit 2 y	Survival Follow-up z
Study Days a :	Day -28 to -1	Day 1	Day 3 (-1 day)	Phase 3 only: Day 5 (± 1 day)	Day 1 (± 3 days)	Day 3 (+ 2 days)	30 days from last dose (± 7 days)	90 days from last dose (± 7 days)	Every 12 weeks (± 14 days)
Additional lab assessments m	X				Pre-dose m				
Urinalysis (dipstick) n	X	Pre-dose			Pre-dose				
Serology o	X								
Tumor HPV status p	X								
PK and immunogenicity assessments		Phase 2 portion of the study: refer to Table 8 Phase 3 portion of the study: refer to Table 9							
[REDACTED]		[REDACTED]							
Tumor assessment q	X	First year from date of randomization, imaging every 6 weeks (± 7 days), or more frequently if clinically indicated. After 1 year from randomization, imaging every 9 weeks (± 14 days) for patients who remain on treatment.				For patients who discontinue study drug without progression, monitor every 6 weeks (± 7 days) (or every 9 weeks ± 14 days 1 year after randomization) until: 1) Start of new anticancer treatment, 2) Disease progression by BICR, 3) Death, 4) Withdrawal of consent, or 5) End of the study, whichever occurs first. The first follow-up assessment should occur 6 weeks (± 7 days) from the last scheduled on-treatment imaging time point (or 9 weeks ±14 days from the last scheduled on-treatment imaging time point 1 year after randomization).			

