### **8.1.2 Tumor Imaging During the Study**

Imaging should be performed every 6 weeks (42 days  $\pm$  7 days) from the date of randomization or more frequently if clinically indicated. One year after randomization, patients who remain on treatment will have imaging performed every 9 weeks ( $\pm$  14 days). This imaging schedule should be maintained regardless of treatment delays or other changes in treatment schedule.

The scan for confirmation of partial response or complete response may be performed at the earliest 4 weeks after the date the response was first documented, or at the next scheduled scan (ie, 6 weeks later), whichever is clinically indicated. Imaging should then return to the original schedule beginning with the next protocol-specified time point.

Patients who obtain a confirmation scan at 4 weeks do not need to undergo the next scheduled imaging assessment if it is due  $<$  4 weeks later; imaging may resume at the subsequent scheduled time point.

Continue to perform imaging until whichever of the following occurs first:

- Initial site-assessed disease progression is verified by the central imaging vendor.
- The start of new anticancer treatment
- Withdrawal of consent
- Death
- The end of the study

Note: If the site-assessed disease progression is verified by the central imaging vendor, it is the discretion of the Investigator to continue to treat the patient (see Section 6.2.5) and follow the regular imaging schedule intervals until progression is confirmed provided the patient meets the conditions detailed in Section 8.1.3.

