### 11.5 Efficacy Analyses

#### 11.5.1 Primary Efficacy Analyses

ORR is defined as the percentage of patients with a confirmed best overall response of CR or PR by RECIST 1.1 per BICR in the ITT population. As a primary efficacy endpoint, ORR will be tested at an overall alpha level of 0.001. The Cochran Mantel Haenszel (CMH) test statistic will

be used to compare the proportion of patients with an objective response between the 2 treatment arms.

The ORR difference between the two treatment arms with its 95% and 99.5% confidence intervals (CIs) will be calculated by the CMH test statistic using the normal approximation. The ORR and its corresponding 95% exact CI will also be calculated by Clopper-Pearson method for each arm. Patients who do not have on-study tumor assessments to evaluate response status will be counted as non-responders.

Overall survival (OS) is defined as the time between the date of randomization and the date of death due to any cause. A patient who does not have a date of death will be censored on the last date for which the patient was known to be alive.

As another primary efficacy endpoint, OS will be evaluated at an overall alpha level of 0.049 if ORR is not significant and at 0.05 if ORR is significant. The regular stratified log-rank test will be used at IA2 to compare overall survival between the two treatment arms. At the final analysis, the weighted combination version of the stratified log-rank test with prespecified weights (Lehmacher 1999) will be used to compare overall survival between the two treatment arms. A stratified Cox proportional hazards model with treatment as the single covariate will be used to estimate the hazard ratio and corresponding 95% CI. The weighted combination approaches as specified in Brannath et. al. (Brannath 2006) will be performed as an exploratory analysis. The Kaplan-Meier method will be used to summarize overall survival per arm, including Kaplan-Meier curves, medians with corresponding 95% CIs, etc.

At the first interim analysis, ORR will be assessed for futility: ORR futility assessment (ie, the difference in ORR proportions is  $\geq 0\%$  [bempegaldesleukin plus pembrolizumab minus pembrolizumab monotherapy]) will serve as a gate to proceed to the Phase 3 portion of the study.

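### The IA1 go/no-go gate reads confirmed ORR at a projected one month after the last Phase 2 patient, when on scheduled scans about 37 to 45 of 200 patients cannot yet have a confirmed response

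*Protocol*

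**What the plan says.** - **Endpoint.** Protocol Section 11.5.1: "ORR is defined as the percentage of patients with a confirmed best overall response of CR or PR by RECIST 1.1 per BICR". The analysis set is ITT. No other response definition is given for IA1.
- **Role of IA1.** In the same section, an ORR difference of at least 0% "will serve as a gate to proceed to the Phase 3 portion of the study".
- **Timing.** Section 11.2 places IA1 "at least one month after the last patient of the Phase 2 portion has been randomized into the study". Section 11.2.1 turns that into a 14-month projection: once 200 patients have been accrued over 10 months, it allows "one month of ORR follow-up, and 3 months for data cleaning".
- **Scans.** Table 1 (Section 1.2): "First year from date of randomization, imaging every 6 weeks (± 7 days), or more frequently if clinically indicated". Under Section 8.1.2 the confirming scan "may be performed at the earliest 4 weeks after the date the response was first documented", or falls at the next scheduled scan 6 weeks later.
- **Missing assessments.** Section 11.5.1: "Patients who do not have on-study tumor assessments to evaluate response status will be counted as non-responders".

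The visible text sets no minimum follow-up beyond one month and no response-evaluable subset for IA1. The SAP was written after the study was discontinued. It covers only listings for the single patient enrolled and adds nothing on IA1.

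**The concern.** One month is about 4.3 weeks, which is shorter than the interval to the first scheduled scan even at its early limit of week 5. The last patients enrolled therefore reach the projected cut with no scheduled scan, and those enrolled somewhat earlier have at most one scan that cannot yet be confirmed. Neither group can contribute a confirmed response, but both stay in the ITT denominator.

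The gate decides whether about 300 more patients are randomized. It looks only at the sign of a difference between two groups of about 100. Shrinking both observed rates pulls the expected difference towards zero faster than it reduces the noise, so the sign becomes less reliable in both directions.

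**Working it through.** **1. The plan's own figures.** The IA1 date is 10 + 1 + 3 = 14 months, and the 4-month enrollment pause is the last two terms. The ORR power in Section 11.2.1 (250 per arm, 19% vs 39%, two-sided 0.001) reproduces. The standard error is √[(0.19×0.81 + 0.39×0.61)/250] = 0.0396, so 0.20/0.0396 − 3.29 = 1.76, giving 96.1%. The pooled version gives 95.3%. The plan states about 96%.

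**2. Accrual before the cut.** Section 11.2.2 gives a staged ramp over 5 months to 35 per month. With 200 patients in 10 months, months 6–10 supply 5 × 35 = 175, which leaves 25 for the ramp. The 25 is inferred, not stated. How it is spread does not matter here, because every count below falls within the 175.

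**3. Patients with less than w weeks of follow-up at a one-month cut.** N(w) = 35 × (w/4.348 − 1), with 4.348 weeks per month.

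| w (weeks) | What needs w weeks | N(w) of 200 |
|---|---|---|
| 5 | first scan, early edge of window | 5 |
| 6 | first scan, nominal | 13 |
| 9 | confirmed response, earliest in window (5 + 4) | 37 (19%) |
| 10 | confirmed response, nominal (6 + 4) | 45 (23%) |
| 12 | confirmed at next scheduled scan (6 + 6) | 62 (31%) |

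At a flat 20 per month, as a sensitivity case only, the 9- and 10-week counts are 21 and 26.

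**4. Effect on the gate.** Let f be the share of eventual responders already countable at the cut, equal in both arms. Observed responders are binomial with 100 patients per arm and rate f × p. The gate fails if Arm A has fewer responders than Arm B. Response timing is an assumption:

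- *Fast:* all responses are first seen at the first scan and confirmed 4 weeks later. At 9 weeks f = 1 − 37.4/200 = 0.813. At 10 weeks f = 1 − 45.5/200 = 0.773.
- *Slow:* 60/30/10% are first seen at weeks 6/12/18 and confirmed at the next 6-weekly scan. With N(12), N(18), N(24) = 61.6, 109.9, 158.2, f = 0.6×0.692 + 0.3×0.451 + 0.1×0.209 = 0.571.

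Probability of failing the gate, from exact binomial sums:

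| Scenario | f | 25% vs 19% | 29% vs 19% | 39% vs 19% |
|---|---|---|---|---|
| Mature data | 1 | 13.3% | 4.0% | 0.06% |
| As planned, fast, 9 weeks | 0.813 | 16.0% | 6.0% | 0.2% |
| As planned, fast, 10 weeks | 0.773 | 16.6% | 6.6% | 0.3% |
| As planned, slow | 0.571 | 20.0% | 9.9% | 1.1% |
| Unconfirmed counted, fast to slow | 0.934–0.813 | 14.2–16.0% | 4.7–6.0% | 0.1–0.2% |
| Cut at 2.5 months, fast to slow | 1–0.834 | 13.3–15.6% | 4.0–5.8% | 0.06–0.2% |

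The error also runs the other way. If the combination is truly worse (14% vs 19%), the gate is passed 19.5% of the time with mature data, 23.7% in the fast 10-week case and 28.4% in the slow case. With no true difference the pass probability barely moves (53.6% to 54.0% in the fast 10-week case).

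The unconfirmed rows ignore responses that would later fail confirmation, so they are somewhat optimistic.

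**The case against.** Several points against the concern stand and set its limits.

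- **The design effect is safe.** The protocol sizes ORR for 39% vs 19%, and there the gate fails about 1% of the time or less even in the slow case. The effects 25% and 29% are chosen here for illustration; the protocol does not use them.
- **No bias in direction.** Follow-up is lost equally in two randomized arms and the boundary is zero, so the expected sign does not change. Most of the 16–20% at 25% vs 19% is the 13% already present with mature data.
- **One month is a floor and a projection.** The rule permits a later cut without amendment. The answer is that a floor shorter than the first scan interval protects nothing, and the timeline is built on exactly that floor.
- **Scans may come earlier.** The window allows 9 weeks, and unscheduled imaging is allowed if clinically indicated. A reader might infer that these patients can never count as responders whatever their outcome. The documents support only that they cannot on scheduled scans at the projected cut.
- **The non-responder rule is narrower than it looks.** It covers patients with no on-study assessment, about 13 at the nominal schedule. The rest of the 37 to 45 fail to count only because the endpoint requires confirmation.
- **The pause is fully used.** One month of follow-up and three of cleaning fill it, and nothing in the documents shows that faster cleaning is feasible.
- **Some text is not visible.** Figure 2 and Section 11.8 cannot be seen, and the DMC charter was not supplied. They may add IA1 detail, but they would not alter the one month stated in Section 11.2.1.

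**Conclusion.** The mismatch between a confirmed endpoint and one month of projected follow-up is in the text. If IA1 is cut as projected and accrual reaches 35 per month, about 37 to 45 of 200 patients (19–23%) cannot have a confirmed response on scheduled scans, and about 13 have not reached week 6.

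The cost is lost information, not bias. The chance of wrongly stopping rises by about 3 to 7 percentage points at 25% vs 19% and 2 to 6 points at 29% vs 19%, and wrong continuations rise too. These sizes rest on the assumed response timings, equal loss in both arms and 100 patients per arm. A reader might infer that the gate is likely to stop the combination at its planned effect; the figures do not support that.

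This is a worthwhile, inexpensive improvement to a futility-only gate. Because the study has been discontinued, it bears on the design as written and on any reuse of it.

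**What to change.** Change Sections 11.2.1 and 11.5.1 and the DMC charter in one of two ways, for the IA1 gate only:

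1. **Count unconfirmed as well as confirmed CR/PR by blinded central review.** Failure risk becomes about 14–16% at 25% vs 19% and 5–6% at 29% vs 19%. The cost is a slightly looser response definition at a futility look.
2. **Replace the one-month minimum with a data cut at least 10 to 12 weeks after the last Phase 2 randomization**, with central reads and cleaning done on a rolling basis inside the pause where feasible. Failure risk becomes about 13–16% and 4–6%. Ten to 12 weeks is 2.3 to 2.8 months, so about 1.5 months of a 4-month pause remain for cleaning instead of 3; otherwise the pause lengthens slightly.

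In either case state the IA1 response definition and minimum follow-up explicitly. Keep confirmed ORR for the 0.001 test at IA2. Neither option spends alpha or adds patients.

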**11.2.2 Sample Size Justification for OS**

The study is powered to detect an improvement in OS for bempegaldesleukin combined with pembrolizumab compared with pembrolizumab monotherapy. An initial total of 298 OS events are needed to detect a hazard ratio (HR) of 0.7 with 85% power at a 2-sided significance level of 0.049. Assuming a median OS time for the pembrolizumab arm of 12.3 months (Burtness 2019), with a total sample size of 500, it is projected the total study duration is up to 52 months to reach 393 OS events (after an initial varying staged incremental accrual in the first 5 months to 35 patients per month, then a 4-month enrollment pause after 200 patients have been randomized

and resumed at an initial varying staged incremental accrual in the first 3 months to 35 patients per month until 500 patients are randomized).

One interim analysis of OS is planned for this study at IA2. The interim analysis is projected to occur at 32 months from the first patient randomized into the study. The stopping boundaries at interim and final analyses will be derived based on the number of deaths using O'Brien and Fleming alpha spending function in software EAST 6.5. The detailed alpha spending and statistical significance level at each analysis below are for the planned number of events. If the actual number of events at the time of the analysis is different from the planned one, the actual alpha and statistical significance level will be adjusted using O'Brien and Fleming alpha spending function in software EAST 6.5.

There are two possible testing scenarios at IA2 for OS:

1. The ORR difference is statistically significant at IA2 at alpha level of 0.001.

The overall Type I error rate is 0.05 for the primary endpoint OS and OS will be tested at alpha level of 0.022 at IA2. If the observed HR is tested statistically significant in favor of the combination of treatments, OS benefit will be concluded. Otherwise, OS will be tested at alpha level of 0.028 at the final analysis (FA) corresponding to the statistical significance level of 0.044 calculated based on the correlation of the interim and final combination test statistic.

2. The ORR difference is not statistically significant at IA2.

The overall Type I error rate is 0.049 for the primary endpoint OS. OS will be tested at alpha level of 0.021 at IA2. If the observed HR is tested statistically significant in favor of the combination of treatments, then OS benefit will be concluded. Otherwise, the HR will be tested at alpha level of 0.029 at the final analysis corresponding to the statistical significance level of 0.043 calculated based on the correlation of the interim and final combination test statistic.

The detailed calculation will be provided in the SAP.

At IA2, if OS is not statistically significant, then conditional power will be calculated. The adaptive method in Liu and Hu ([Liu 2016](#)) and Mehta and Pocock ([Mehta 2011](#)) will be used to determine the number of OS events needed to target approximately 85% to 90% conditional power for the final analysis. The final analysis will be triggered when this re-estimated number of OS events is reached.

The minimum and maximum number of OS events for the final analysis are 298 and 393, respectively. The minimum event size is calculated to achieve 86% power with  $\alpha = 0.049$  (two-sided) assuming an exponential distribution in each treatment arm and an HR = 0.7 with median OS for the pembrolizumab arm of 12.3 months ([Burtness 2019](#)). The maximum event size is determined to detect the minimum clinically meaningful effect of HR around 0.82.

The detailed sample size adaptation rules based on conditional power will be described in an appendix of the Data Monitoring Committee (DMC) Charter, which will not be accessible to the study team or sites to prevent introduction of any potential bias; however, the operational procedures will be described in the DMC Charter, which is accessible to the study team.

The key secondary endpoints will be tested hierarchically given statistical significance of OS. Further details of the testing procedure will be described in the SAP.

Figure 2 provides the study flow and decision-making time points for the primary endpoints.

